### AIM

The overall aim of the PRODICA-study is to increase the knowledge, for the impact of diet on prostate tumor proliferation.

### HYPOTHESIS

- In men diagnosed with intermediate risk-level prostate cancer, the addition of phytoestrogenrich foods containing 200 mg phytoestrogens per day in six weeks, gives a reduced prostate tumor proliferation compared to an absence of the addition of phytoestrogen-rich foods during the same period.
- 2) If the effect of phytoestrogens on prostate tumor proliferation exists, it is modified by a SNP in the promoter region of the estrogen-beta-gene (rs 2987983-13950).

### STUDY DESIGN

The study design is shown in Figure 1. Men diagnosed with intermediate-risk prostate cancer T1–T2 (Gleason score <8, PSA <20), scheduled for radical prostatectomy, are identified at the Sahlgrenska University Hospital. Interested men are contacted by phone and a first meeting is scheduled. At the meeting the participants receive verbal and written information and sign an informed consent. A food frequency questionnaire including dietary and living habits and supplements are filled in and baseline blood samples are taken. The men are randomized to a diet or a control group through a closed envelop. All participants receive general dietary advice according to the Swedish National Food Agency (1). Participants are instructed to avoid supplements but no other dietary restrictions are given. The diet group receive a food package including food items high in phytoestrogens. Recipes and serving suggestions for the study diet are also given. The intake of the food items gradually steps up according to a schedule and the items are eaten in specific amounts until the surgery.

The participants are contacted by phone once during the study and a 24-hour recall is performed. The interview is made to control compliance in the study group and to estimate the intake of phytoestrogens in the control group. Near to surgery a similar food frequency questionnaire is filled in and endpoint blood samples are taken. Prostate biopsies are taken at the surgery. Hormones and PSA are analyzed from baseline and endpoint blood samples. The expression of androgen receptor and estrogen receptor alfa and beta are analyzed in tumor material. Tumor proliferation is calculated by ki-67 from prostatectomy specimens at surgery.

#### NUMBER OF SUBJECTS

The person time studied will be 203 person moments. Interim analyzes will be made when there is data to analyze 100 person moments.

### INCLUSION CRITERIA

- Patients with prostate cancer T1–T2, Gleason score <8, prostate-specific antigen (PSA) <20
- scheduled for radical prostatectomy.

### EXCLUSION CRITERIA

Ongoing hormone therapy Difficult physical or psychological conditions or diminished cognitive function Allergy or intolerance of the intervention foods

### DATA MANAGEMENT

#### **Definition of primary outcome**

### **Ki-67**

Tumor proliferation rate (Ki-67) is measured in prostatectomy specimens from the surgery. The ratio of stained prostate cancer nuclei is calculated in five different areas and the median, mean, and max

### Analysis plan: PRODICA, [name]

values are calculated

Analyze of prostatectomy specimens from the surgery, variables: **ki67\_median** (median value of ki-67) **ki67\_mean** (mean value of ki-67) **ki67\_max** (max value of ki-67) Above variables will be dichotomized according to the median value in the study population:ki67\_median\_cat (0/1) ki67\_mean\_cat (0/1) ki67\_max\_cat (0/1)

### Definition of secondary outcomes

Levels of PSA are analyzed from blood samples taken at the inclusion meeting (baseline) and in connection with another visit within one week before surgery (endpoint). The difference is calculated between endpoint and baseline.

**PSA** 

PSA\_total\_BL (total PSA levels at baseline)
PSA\_total\_EP (total PSA levels at endpoint)
PSA\_total\_diff (difference in total PSA levels, endpoint-baseline)
PSA\_total\_diff\_cat (total PSA difference endpoint-baseline, decreased/unchanged=0, increased=1)

PSA\_ratio\_BL (PSA ratio free/total at baseline)
PSA\_ratio\_EP (PSA ratio free/total at endpoint)
PSA\_ratio\_diff (difference in total PSA levels, endpoint-baseline)
PSA\_ratio\_diff\_cat (PSA ratio diff endpoint-baseline, decreased/unchanged=0, increased=1))

### Hormones

Concentrations of testosterone, estradiol, sex hormone binding globulin (SHBG), and IGF-1 will be analyzed in serum at endpoint and baseline. The difference is calculated between endpoint and baseline.

Estradiol\_BL (Estradiol levels at baseline) Estradiol\_EP (Estradiol levels at endpoint) Estradiol\_diff (difference in Estradiol levels, endpoint-baseline) estradiol\_diff\_cat (Estradiol difference endpoint-baseline, decreased/unchanged=0, increased=1)

Testosterone\_BL (Testosterone levels at baseline) Testosterone\_EP (Testosterone levels at endpoint) Testosteron\_diff (difference in Testosteron levels, endpoint-baseline) testo\_diff\_cat (Testosteron difference endpoint-baseline, decreased/unchanged=0, increased=1)

**IGF1\_BL** (IGF1 levels at baseline) **IGF1\_EP** (IGF1 levels at endpoint)

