### Covariates to test (possible confounding factors):

- Energy\_kcal\_EP\_3 (total energy intake at endpoint, categorized in tertiles)
- Sum\_satured\_fat\_EP\_3 (sum of saturated fats (g) at endpoint, categorized in tertiles)
- Fat\_fish\_group\_EP (categorized intake of fat fish at endpoint)
- Calcium\_EP\_3 (intake of calcium at endpoint, categorized in tertiles)
- Physical\_activity\_BL\_group (categorized physical activity at baseline)
- f47\_1\_EP (changed physical activity during intervention)
- Biopsies\_cancer (percent of biopsies with cancer at diagnosis)
- gleason\_cat (categorized Gleason score at diagnosis)
- gleason\_cat\_rp (categorized Gleason score at surgery)
- rp\_teritargradjanej (categorized tertiary Gleason degree at surgery)
- Age\_inclusion (continuous age at baseline)
- BMI\_group (BMI at baseline in groups)
- Weight\_diff (difference in weight between endpoint and baseline)
- smoking (categorized smoking at baseline)
- heredity (categorized heredity at baseline)
- Zinc\_EP\_3 (intake of zinc at endpoint, categorized in tertiles)
- Alcohol\_EP\_3 (intake of alcohol at endpoint, categorized in tertiles)
- Sum\_monosat\_fat\_EP\_3 (intake of monounsaturated fatty acids at endpoint, categorized in tertiles)
- Sum\_polysat\_fat\_EP\_3 (intake of polyunsaturated fatty acids at endpoint, categorized in tertiles)
- red\_meat\_EP\_3 (intake of red meat at endpoint, categorized in tertiles)
- vegetables\_all\_EP\_3 (intake of vegetables at endpoint, categorized in tertiles)
- fruit\_all\_EP\_3 (intake of fruits at endpoint, categorized in tertiles)
- Vit\_E\_EP\_3 (intake of vitamin E at endpoint, categorized in tertiles)

• Finasteride (intake of Finasteride under intervention, no=0, yes=1)

Pearson or Spearman correlation coefficient will be used to evaluate whether dietary covariates are correlated. If the correlation coefficient between two covariates in the model or between covariates and the main exposure are higher than 0.6, multicolinearity issues is considered, eventually one of the covariates will be excluded from the model.

Model building:

The association between intake of phytoestrogens and tumor proliferation will evaluated by regression models, providing estimate of risk difference (RD) relative risk (RR) and corresponding 95% confidence intervals.

Crude models:

C0: Ki-67

C1: C0 + Group\_intervention C2: C0 + Phytoestogens\_EP C3: C0 + Isoflavones\_EP C4: C0 + Lignans\_EP C5: C0 + Coumestrol\_N58\_EP

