C02: PSA\_total\_diff C12: C02 + Group\_intervention C22: C02 + Phytoestogens\_EP C32: C02 + Isoflavones\_EP C42: C02 + Lignans\_EP C52: C02 + Coumestrol N58 EP

C03: PSA\_ratio\_diff C13: C03 + Group\_intervention C33: C03 + Phytoestogens\_EP C43: C03 + Isoflavones\_EP C53: C03 + Lignans\_EP C63: C03 + Coumestrol N58 EP

C04: estradiol\_diff\_cat C14: C04 + Group\_intervention C34: C04 + Phytoestogens EP C44: C04 + Isoflavones\_EP C54: C04 + Lignans\_EP C64: C04 + Coumestrol N58 EP

C05: testo\_diff\_cat C15: C05 + Group\_intervention C35: C05 + Phytoestogens\_EP C45: C05 + Isoflavones\_EP C55: C05 + Lignans\_EP C65: C05 + Coumestrol\_N58\_EP

 $\underline{C0_6:} testo_estrad_ratio_diff$   $C1_6: C0_6 + Group\_intervention$   $C3_6: C0_6 + Phytoestogens\_EP$   $C4_6: C0_6 + Isoflavones\_EP$   $C5_6: C0_6 + Lignans\_EP$   $C6_6: C0_6 + Coumestrol\_N58\_EP$ 

C07: testo\_SHBG\_ratio\_diff C17: C07 + Group\_intervention C37: C07 + Phytoestogens\_EP C47: C07 + Isoflavones\_EP C57: C07 + Lignans\_EP C67: C07 + Coumestrol\_N58\_EP

Final model:

Which covariates included in the model will be based on:

- 1) If a known risk factor for the outcome (based on previous subject matter knowledge and with the help of Directed Acyclic Graphs)
- 2) If differs between groups of exposure
- 3) proportional ( $\geq 10\%$ ) change in  $\beta$ -coefficients

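### Estradiol and testosterone are analysed only as risen or not risen, and no serum outcome is sure to be adjusted for its own baseline, so the randomised comparison loses precision

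*SAP*

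**What the plan says.** Under Definition of secondary outcomes, PSA is measured at inclusion and within a week before surgery, and "The difference is calculated between endpoint and baseline". The Hormones section treats the serum hormones in the same way.

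For estradiol and testosterone that section defines two outcome variables each:

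- a continuous change, which for testosterone is the "difference in Testosteron levels, endpoint-baseline";
- a binary version split at zero change, "Estradiol difference endpoint-baseline, decreased/unchanged=0, increased=1" and "Testosteron difference endpoint-baseline, decreased/unchanged=0, increased=1".

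The list of crude models then takes only the binary versions: "C04: estradiol\_diff\_cat" for estradiol and "testo\_diff\_cat C15: C05 + Group\_intervention" for testosterone. `Estradiol_diff` and `Testosteron_diff` head no model. Total PSA, PSA ratio, testosterone/estradiol and testosterone/SHBG are listed under their continuous change variables. Every crude model adds a single exposure term.

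The list headed "Covariates to test (possible confounding factors" has 24 entries, and none is a baseline PSA or hormone value. Under Final model, the text beginning "Which covariates included in the model will be based on" gives three rules: known risk factor (subject knowledge and directed acyclic graphs), difference between exposure groups, and a change of at least 10% in the coefficient.

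**The concern.** There are two separate losses, and the first is the larger.

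**The split at zero.** Keeping only the sign counts a trivial fluctuation the same as a large change. No tolerance around zero is set, so for men with little real change, noise decides the category. The SAP gives no reason for reducing these two hormones to a sign while the other serum outcomes in the list stay continuous.

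**No assured baseline term.** Under randomisation a change score is unbiased, but it is generally less precise than adjusting the endpoint for its baseline, and it is sensitive to chance imbalance at baseline. The three covariate rules do not close the gap. The first is discretionary. The second depends on chance imbalance. The third looks for confounding rather than precision, so a strongly prognostic baseline that barely moves the coefficient can be left out.

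At stake is a real effect of the diet on estradiol or testosterone going undetected although the samples could show it. The genotype section repeats the same models within strata, so the loss carries into smaller groups.

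**Working it through.** **Inputs.** The SAP gives a study size of 203 person moments, but no baseline-endpoint correlation (ρ), SD, or target power for these outcomes. There is no figure of the plan's own to reproduce. Assumed here: two-sided α of 0.05, 1:1 allocation, ρ of 0.5, 0.7 and 0.9 and, for steps 1 and 2, equal variances and normal changes.

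**Step 1: change score against baseline adjustment.** With unit variance at both times, Var(change) = 2(1−ρ) and the residual variance after baseline adjustment is 1−ρ². The efficiency of the change score is (1−ρ²)/[2(1−ρ)] = (1+ρ)/2.

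**Step 2: sign against change score.** A split with share p on one side keeps φ(z_p)²/[p(1−p)] of the information in a normal change: 2/π = 0.637 at 50%, 0.622 at 60%, 0.576 at 70%, 0.49 at 80% and 0.34 at 90%. The figure of 64% is therefore the best case under normality.

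**Step 3: combine and convert to power.** Where the baseline-adjusted analysis has 80% power, the noncentrality is 1.96 + 0.84 = 2.80, and another analysis has power Φ(2.80·√efficiency − 1.96).

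| ρ | Change-score efficiency | Its power | Sign efficiency (50% split) | Its power |
|---|---|---|---|---|
| 0.5 | 0.75 | 68% | 0.637 × 0.75 = 0.48 | 49% |
| 0.7 | 0.85 | 73% | 0.637 × 0.85 = 0.54 | 54% |
| 0.9 | 0.95 | 78% | 0.637 × 0.95 = 0.61 | 59% |

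**Step 4: the same question from the other side.** Assume 100 men per arm and an effect giving the continuous change score 80% power: 2.80 × √(2/100) = 0.396 SD of change. If 50% of controls rise, then Φ(0.396) = 65.4% rise in the diet arm. The binary analysis has about 60% power and needs about 161 men per arm instead of 101. With 30% of controls rising it has 59% power (165 per arm); with 70%, 52% (193 per arm). Baseline adjustment would raise the 80% to 90%, 86% and 82% at ρ of 0.5, 0.7 and 0.9.

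**Step 5: sensitivity.**

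- Unequal variances: with k = SD(endpoint)/SD(baseline), the change-score efficiency is k²(1−ρ²)/(k²+1−2ρk). Over ρ of 0.5 to 0.9 this is 0.57–0.64 for k = 0.8 and 0.89–1.00 for k = 1.25.
- Heavier tails: the sign's efficiency against the raw mean difference is 4f(0)²·Var. It is 0.76 for t with 10 df, 0.96 for t with 5 df and 2.0 for the Laplace distribution.
- Chance imbalance: a baseline difference of 0.2 SD shifts the change-score contrast by (1−ρ) × 0.2 SD, which is 0.10 SD at ρ = 0.5 and 0.02 SD at ρ = 0.9.

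**The case against.** The two parts are unequal. Change score against baseline adjustment is a matter of efficiency for secondary outcomes, the loss is only 5% at ρ = 0.9, and the first covariate rule could bring a baseline value in. This stands as a limit on size, particularly for total PSA if its two measurements correlate highly. It does not make the adjustment certain.

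The size of the loss is not in the document, and heavy tails can remove it. This also stands: against a raw mean difference the sign can do as well or better when changes are very heavy-tailed. It is a reason to fix a log scale for skewed values; it does not support analysing the sign.

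Estradiol and testosterone do enter continuously through the ratio outcomes, and the Statistical models section offers a t-test or Mann-Whitney test for continuous variables. A ratio does not isolate either hormone, however, and those tests are limited to the variables listed after that sentence, where the two continuous differences do not appear.

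The SAP promises risk differences and relative risks, which suit binary outcomes, so the PSA models might be meant as binary too. That sentence concerns tumour proliferation, and the PSA models carry the continuous variable names. If the binary PSA versions were fitted after all, the loss would extend to PSA. The genotype section also measures interaction by risk differences, which already does not fit the continuous outcomes in the list. The fix has to cover this.

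**Conclusion.** The concern holds. The text is clear that the two single hormones are modelled only by the sign of change and that baseline adjustment is not assured for any serum outcome.

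The split is the larger loss: at best about 64% of the change score's information is kept under normal changes, and about 48–61% of that in a baseline-adjusted analysis for ρ of 0.5 to 0.9. The missing baseline term alone costs 5–25% over the same range with equal variances. These sizes rest on assumed correlations, variances and distributions.

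The matter is one of precision, not bias. It is confined to the secondary serum outcomes: Ki-67 and the tissue receptor and gene expression outcomes have no baseline measurement and are unaffected. The plan should be changed on this point because the remedy uses data already collected.

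**What to change.** For the `Group_intervention` models of total PSA, PSA ratio, estradiol, testosterone and the two hormone ratios:

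- Regress the endpoint value on randomised group and the outcome's own baseline value on the same scale, using logs if values are skewed.
- Report the adjusted mean difference, or the ratio of geometric means if logged, with a 95% CI.
- Keep the increased/not-increased variables as description only.
- In the genotype section, state the interaction for these outcomes on the scale of the new model (product term in the same linear model) in place of a risk difference.
- SHBG and IGF-1 have no model of their own. If they are to be compared between arms, use the same model.

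This covers the randomised comparison only. The models on reported intake of phytoestrogens, isoflavones, lignans and coumestrol are non-randomised and are a separate matter.

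The cost is SAP wording, minor programming and one degree of freedom per model. Baseline and endpoint variables already exist for PSA and the single hormones. Those for the two hormone ratios must be built from components that are already defined. No new samples are needed.

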### Analysis plan: PRODICA, [name]

IGF1\_difference (difference in IGF1 levels, endpoint-baseline)
SHBG\_BL (SHBG levels at baseline)
SHBG\_EP (SHBG levels at endpoint)
SHBG\_difference (difference in SHBG levels, endpoint-baseline)

testo\_estrad\_ratio\_diff (ratio testosterone/estradiol difference endpoint-baseline)
testo\_SHBG\_ratio\_diff (ratio testosterone/SHBG difference endpoint-baseline)

### Gene expression

The radical prostatectomy tissues are collected at surgery and formalin fixed paraffin embedded. Expression of genes involved in proliferation and ER signal pathways and cell-cycle progression (CCP) gene expression will be analyzed to identify the expression of genes involved in tumorigenesis. Global transcriptome-wide expression array Clariom D® will be used. For analysis of the CCP score, gene expression of the genes involved in CCP based on the Prolaris® gene panel and the Decipher Score. Thereafter, guided and unguided analyses will be performed.

### **Receptors** expression

One benign- and one cancer biopsies are collected at surgery.  $ER\alpha$ ,  $ER\beta$ , and AR mRNA expression will be determined.

**ER\_a** (mRNA levels of estrogen receptor  $\alpha$ ) **ER\_b** (mRNA levels of estrogen receptor  $\beta$ ) **AR** (mRNA levels of androgen receptor)

# **Definition of exposure**

The participants in the intervention group are defined as exposed and the participants in the control group are defined as not exposed.

**Group\_intervention** (0=control, 1=intervention)

Intake of different phytoestrogens at endpoint is based on information from the Food Frequency Questionnaire (FFQ) and the 24-h dietary recall.

**Phytoestogens\_EP\_3** (intake of phytoestrogens at endpoint divided in tertiles, calculated from the FFQ)

Lignans\_EP\_3 (intake of lignans at endpoint divided in tertiles, calculated from the FFQ)

Isoflavones\_EP\_3 (intake of isoflavones at endpoint divided in tertiles, calculated from the FFQ)

Coumestrol\_N58\_EP\_2 (dichotomized intake of coumesterol at endpoint, calculated from the FFQ)

Phyto\_24\_recall\_3 (intake of phytoestrogens at the 24-h dietary recall divided in tertiles)

The concentrations of phytoestrogens (daidzein, enterodiol, enterolactone, equol, genistein, glycetein,

Analysis plan: PRODICA, [name]
----------------------------	--------------

lariciresinol, and secoisolariciresinol) in plasma for a sub-group of participants:

**lignans\_EP\_nmol** (plasma levels of lignans at endpoint=enterolactone+ enterodiol+ lariciresinol+ seco\_EP\_nmol)

**lignans\_BL\_nmol** ((plasma levels of lignans at baseline=enterolactone+ enterodiol+ lariciresinol+ seco\_EP\_nmol)

**isoflavones\_EP\_nmol** (plasma levels of isoflavones at endpoint = daidzein\_EP\_nmol + genistein EP nmol + glycitein EP nmol + equol EP nmol)

**isoflavones\_BL\_nmol** (plasma levels of isoflavones at baseline = daidzein\_EP\_nmol + genistein\_EP\_nmol + glycitein\_EP\_nmol + equol\_EP\_nmol)

**phytoestrogens\_EP\_nmol** (plasma levels of total phytoestrogens at baseline = enterolactone\_EP\_nmol + enterodiol\_EP\_nmol + lariciresinol\_EP\_nmol + seco\_EP\_nmol + daidzein\_EP\_nmol + genistein\_EP\_nmol + glycitein\_EP\_nmol + equol\_EP\_nmol)

phytoestrogens\_BL\_nmol (plasma levels of total phytoestrogens at endpoint =
enterolactone\_BL\_nmol + enterodiol\_BL\_nmol + lariciresinol\_BL\_nmol + seco\_BL\_nmol +
daidzein\_BL\_nmol + genistein\_BL\_nmol + glycitein\_BL\_nmol + equol\_BL\_nmol)

lignans\_diff\_nmol = lignans\_EP\_nmol - lignans\_BL\_nmol

isoflav\_diff\_nmol= isoflavones\_EP\_nmol - isoflavones\_BL\_nmol

phyto\_diff\_nmol= phytoestrogens\_EP\_nmol - phytoestrogens\_BL\_nmol

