### PLANS FOR STATISTICAL ANALYZES

### VARIABLES TO ANALYZE

Created variables (for more details see attached variable list):

BMI (kg/m^2): BMI\_stata = Weight\_inclusion / ((Lenght\_inclusion/100) \* (Lenght\_inclusion/100) BMI\_group = 1= under weight (BMI <18.5); 2= normal weight (BMI 18.5-24.9); 3= Overweight (BMI 25-29.9); 4= Obese class (BMI 30-34.9) 1; 5= Obese class ≥2 (BMI ≥35)

Weight change (kg): Weight\_diff = Weight\_endpoint - Weight\_inclusion

Analysis plan: PRODICA, [name]	Version 2
---------------------------------------	-----------

Compliance (1= compliance >80; 0= compliance <80 %): Compliance 24 recall (based on reported intake of phytoestrogens at the 24-h dietary recall) Compliance intervention 24 r (based on eaten interventions foods reported from at the 24-h dietary recall) Compliance intervention (based on eaten interventions foods reported from at the end of the intervention) Intake of isoflavones (µg): Isoflavones BL = Genistein N56 BL + Daidzein N57 BL + Formononetin N59 BL + Biochanin N60 BL + Equol N75 BL Isoflavones EP = GenisteinN56 EP + Daidzein N57 EP + Formononetin N59 EP + Biochanin N60 EP + Equol N75 EP. Intake of lignans (µg): Lignans BL = SECOtot N61 BL + Matairesinol N62 BL Lariciresinol N71 BL + Pinoresinol N72 BL + Syringaresinol N73 BL + Medioresinol N74 BL + Enterodiol N76 BL + Enterolactone N77 BL Lignans EP=SECOtot N61 EP + Matairesinol N62 EP + Lariciresinol N71 EP + Pinoresinol N72 EP + Syringaresinol N73 EP + Medioresinol N74 EP + Enterodiol N76 EP + Enterolactone N77 EP Intake of phytoestrogens (ug): Phytoestogens BL = (Isoflavones BL + Lignans BL + Coumestrol N58 BL) Phytoestogens EP =(Isoflavones EP + Lignans EP + Coursetrol N58 EP) Level of physical activity: Physical activity BL group = low, moderate or high 1 = Low physical activity (101, 102, 103 or 201 points) 2 = Moderate physical activity (104, 202, 203, 301 or 302 points) 3 = High physical activity (204, 303, 304, 401, 402, 403 or 404 points) Intake of fatty fish: Fat fish group BL:  $0 \le 1$  times/month; 1 = 1-3 times/month;  $2 \ge 1$  times/week Fat fish group EP: 0 = <1 times/month; 1 = 1-3 times/month; 2 = >1 times/week Fat fish diff: Fat fish month EP - Fat fish month BL

Use of antibiotics:

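### The intake models use absolute endpoint phytoestrogen intake without the baseline intake the plan computes, so habitual diet can appear as an effect of intake during the study; the randomized model C1 is unaffected.

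*SAP*

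**What the plan says.** The SAP's Hypothesis section frames the exposure as "the addition of phytoestrogenrich foods containing 200 mg phytoestrogens per day in six weeks", compared with no such addition over the same period.

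The section Definition of exposure gives two kinds of exposure:

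- **Randomized group** (Group_intervention), which enters model C1 for every outcome.
- **Dietary intake**: "Intake of different phytoestrogens at endpoint is based on information from the Food Frequency Questionnaire (FFQ) and the 24-h dietary recall". Total phytoestrogens are defined as "intake of phytoestrogens at endpoint divided in tertiles, calculated from the FFQ". Lignans and isoflavones are treated the same way, and coumestrol is dichotomized.

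Baseline intake is available. Under Study design: "A food frequency questionnaire including dietary and living habits and supplements are filled in and baseline blood samples are taken". Under Variables to analyze, baseline isoflavones and lignans are computed, and the total is "Phytoestogens BL = (Isoflavones BL + Lignans BL + Coumestrol N58 BL" (closing bracket omitted).

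Habitual diet continues through the study: "Participants are instructed to avoid supplements but no other dietary restrictions are given".

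The modelling text says: "The association between intake of phytoestrogens and tumor proliferation will evaluated by regression models". The section on stratification by ERβ alleles then refers to the whole set of models, intake models included, as the analysis of the hypothesis.

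**The concern.** For a control man, endpoint intake is essentially the diet he brought into the study, since nothing was added. For a man in the diet group it is that diet plus the study foods. A model in endpoint intake alone therefore mixes two things: what was added over six weeks, and a habit that may have lasted for years while the tumor developed.

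If habitual intake is associated with Ki-67 for any reason, including other features of the diet or lifestyle, the intake models will show an association even when the added foods do nothing. The SAP groups these models with the analysis of a hypothesis about addition, so the result could be reported as support for the intervention. A negative association would bias the result toward the hypothesis.

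**Working it through.** **Step 1. Trace baseline intake through the plan.**

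| Place in SAP | Baseline phytoestrogen intake? |
|---|---|
| Study design | Questionnaire completed at first meeting |
| Variables to analyze | Isoflavones, lignans and total computed at baseline |
| Definition of exposure | Absent; intake at endpoint or 24-h recall only |
| Models C2-C5 (Ki-67) | Absent; endpoint terms only |
| PSA and hormone intake models | Absent; endpoint terms only |
| Candidate covariates (24 listed) | Absent |

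An endpoint-minus-baseline change is defined for plasma phytoestrogens and for fatty fish, but in the visible text not for phytoestrogen intake. The variable list in Appendix 1 is not shown.

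**Step 2. Who falls in which tertile.** Assume 1:1 allocation and an addition large enough to separate the arms. Controls are 1/2 of the men and the lowest tertile is 1/3, all of them controls. That tertile holds (1/3)/(1/2) = 2/3 of the controls. The remaining third of controls is 1/2 - 1/3 = 1/6 of all men, which is (1/6)/(1/3) = 1/2 of the middle tertile. Controls are thus split between lowest and middle tertile by habitual diet and reporting error, with no addition involved.

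**Step 3. Expected bias in large samples.** All inputs are assumptions except the 200 mg and the median split of Ki-67, which are in the SAP:

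- 400,000 men, allocated 1:1.
- Habitual intake H log-normal, median 1, 5 or 30 mg/day, SD of log 1, stable over time and measured without error.
- Endpoint intake = H + arm × addition × adherence, with adherence averaging about 0.9.
- Latent Ki-67 = -0.3·z(log H) + √(1 - 0.3²)·noise, cut at its median. The addition has no effect.

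| Addition | C1 risk difference | Middle vs lowest | Highest vs lowest |
|---|---|---|---|
| 200 mg | -0.003 to 0.000 | -0.086 to -0.134 | -0.070 to -0.117 |
| 0 mg (component not raised by the foods) | -0.001 to 0.001 | about -0.13 | about -0.26 |

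C1 is correctly near zero. With log baseline intake added, the false differences shrink to between -0.006 and -0.002 (200 mg) and between -0.017 and -0.006 (0 mg).

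**Step 4. False-positive rates at trial size.** Assume habitual median 3 mg/day, SD of log 1, baseline and endpoint questionnaire values each correlated √0.7 with true habit, 200 mg added at about 90% adherence, no true effect, and a linear risk-difference model on dichotomized Ki-67. The SAP gives 203 person moments and no count of men, so 140 to 200 men is also assumed.

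| Correlation of habitual intake with Ki-67 | Middle vs lowest, falsely significant at 5% |
|---|---|
| 0 | about 6% |
| -0.1 | 7-8% |
| -0.2 | 12-13% |
| -0.3 | 18-23% |

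With log baseline intake in the model the rates are about 5-7%. The highest-versus-lowest contrast is less affected, at 4-12% across the same correlations. For a component the study foods do not raise, Step 3 shows the order reversed: highest versus lowest is then the worse contrast.

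**The case against.** A reader might infer that the trial's test of its hypothesis is confounded by habitual diet. The SAP does not support that. Hypothesis 1 compares addition with no addition, C1 makes exactly that comparison for every outcome, and randomization balances habitual diet in expectation. The only product term written out for the genotype interaction also uses the intervention arm.

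The intake models are worded as associations, and total intake from any source is a legitimate observational exposure. Nowhere does the SAP say that C2-C5 estimate the effect of added intake. This argument stands in part: the fault is one of adjustment and labelling. It does not dispose of the point, because the SAP itself groups these models with the analysis of the hypothesis.

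Other limits also stand:

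- No link between habitual intake and Ki-67 is documented. At a correlation of -0.1 the excess over the 6% seen at zero is slight.
- Treating Ki-67 as continuous gives higher rates (23-33% at -0.3), but the SAP dichotomizes Ki-67 and reports risk differences and relative risks, so those rates should not be used.
- The model lines omit the tertile suffix. If total intake were entered as a continuous, untransformed term with 200 mg added, no inflation was found (about 5%). The defined exposures are, however, tertiles.
- The covariate rules admit known risk factors by subject knowledge and causal diagrams, so baseline intake is not strictly barred. It is simply not listed, and nothing ensures its inclusion.

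**Conclusion.** The point holds for the intake models only. They use absolute endpoint intake, the baseline counterpart is computed and left unused in every outcome model, and habitual diet can therefore appear as an effect of intake during the study. C1 is unaffected and remains the valid test of hypothesis 1.

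The size cannot be fixed from the SAP. It ranges from negligible at zero or weak correlation to roughly three to four times the 6% reference rate at a correlation of -0.3 (18/6 = 3; 23/6 ≈ 3.8), for the contrast most affected when 200 mg is added. It rests on assumed allocation, habitual intake, questionnaire accuracy and number of men. The direction of the problem and the benefit of baseline adjustment do not depend on the exact values, provided some correlation exists.

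**What to change.** In the model-building text and the model lists:

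1. Include the matching baseline intake in every intake model for Ki-67, PSA and hormones: Phytoestogens_BL, Isoflavones_BL, Lignans_BL or Coumestrol_N58_BL, on the log scale if skewed.
2. Exempt that term from the 10% change rule and the 0.6 correlation rule. Baseline and endpoint intake may correlate strongly, and the 0.6 rule could then drop the term when it is most needed.
3. State that C1 tests hypothesis 1 and that the intake models are exploratory and observational.
4. If wanted, add endpoint minus baseline intake as a separate sensitivity exposure. It is not interchangeable with baseline adjustment: the two give the same exposure coefficient only when both intakes enter linearly on the same scale, which tertiles do not. It also remains non-randomized.

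The cost is SAP wording and one covariate per model, from data already collected. Intervals widen slightly where baseline and endpoint intake correlate strongly. Because the questionnaire measures habit with error, adjustment reduces the confounding but does not remove it.
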